For depressive symptoms associated with bipolar disorder, the guideline ⁸⁾ issued jointly by the Canadian Network for Mood and Anxiety Treatments and the International Society for Bipolar Disorders recommend the following drugs as first-line treatments: lithium (alone or in combination with divalproex, a selective serotonin reuptake inhibitor [SSRI], or bupropion), lamotrigine, quetiapine, olanzapine-fluoxetine combination, divalproex (in combination with an SSRI or bupropion). In Japan, the treatment guideline by the Japanese Society of Mood Disorders ⁹⁾ recommends quetiapine, lithium, olanzapine, and lamotrigine as first-line treatments; however, only olanzapine is approved for this indication. Moreover, these

currently available drugs are known to have side effects. For example, olanzapine and quetiapine are associated with adverse reactions such as increased weight and abnormal glucose metabolism. Lamotrigine may cause adverse reactions such as serious skin disorders (eg, Stevens-Johnson syndrome). Lithium may cause adverse reactions such as renal disorder and thyroid dysfunction, and furthermore it requires blood concentration monitoring to prevent intoxication.

Lurasidone HCl (SM-13496) is a novel atypical antipsychotic synthesized by Sumitomo Pharmaceuticals Co., Ltd. (currently Sumitomo Dainippon Pharma Co., Ltd.). It has a high binding affinity for dopamine D₂ and serotonin 5-HT_{2A} receptors, which relate to antipsychotic effects, and 5-HT₇ receptor, which may relate to antidepressant effect and cognitive function¹⁰⁾, and the 5-HT_{1A} receptor, which may relate to anxiolytic effect and cognitive function¹⁰⁾. Therefore, lurasidone is expected to have not only antipsychotic effects but also antidepressant and anxiolytic effects.

In the United States and Canada, lurasidone has been approved for the treatment of schizophrenia. In Europe, an application for marketing approval was filed in 2012. In Japan, a multinational phase 3 study in patients with schizophrenia is ongoing.

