2.2 Secondary objectives

The secondary objectives of the study are as follows;

- 1) To evaluate the efficacy of SM-13496 (20-60 and 80-120 mg/day) monotherapy for 6 weeks in patients with depressive symptoms associated with bipolar I disorder by assessing the following
 - Change from baseline in the Clinical Global Impression: Bipolar Version - Severity of Illness (CGI-BP-S) (depression) score at Week 6
 - Change from baseline in the Sheehan Disability Scale (SDS) total score at Week 6
 - The response rate and the remission rate
- 2) To evaluate the time course of efficacy of SM-13496 (20-60 and 80-120 mg/day) monotherapy for 6 weeks in patients with depressive symptoms associated with bipolar I disorder by assessing the change from baseline in the MADRS total score and in the CGI-BP-S (depression) score
- 3) To evaluate the following
 - The efficacy for anxiety symptoms associated with bipolar I disorder by assessing the change from baseline in the Hamilton Rating Scale for Anxiety (HAM-A) total score at Week 6
 - The efficacy for manic symptoms associated with bipolar I disorder by assessing the change from baseline in the Young Mania Rating Scale (YMRS) total score at Week 6

- 4) To evaluate the overall safety of SM-13496 (20-60 and 80-120 mg/day) by assessing the following
 - Adverse events, adverse drug reactions
 - Laboratory measures
 - Vital signs and electrocardiography (ECG) measurements
- 5) To evaluate the influence on the extrapyramidal symptoms by assessing the following
 - Extrapyramidal adverse events, extrapyramidal adverse drug reactions
 - Proportion of patients using concomitant antiparkinson drugs
 - Change from baseline in the Drug-Induced Extrapyramidal Symptoms Scale (DIEPSS) total score (except for the overall severity score) at the final assessment
 - Change from baseline in the individual DIEPSS symptoms scores at the final assessment
- 6) To evaluate the influence on the following
 - QTc
 - Body weight (change from baseline in body weight at the final assessment)
 - Prolactin (change from baseline in serum prolactin concentration at the final assessment)
 - Glucose metabolism (change from baseline in fasting blood glucose, HbA1c, and glycoalbumin at the final assessment)
 - Lipid metabolism (change from baseline in total cholesterol, LDL cholesterol, HDL cholesterol, and triglyceride at the final assessment)

3. Study design and flowchart

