9.7.6 Laboratory tests, vital signs, body weight, and 12-lead ECG

Summary statistics for laboratory tests, vital signs, body weights, and 12-lead ECG parameters will be provided by treatment group. Continuous variables will be summarized using descriptive statistics of number of patients, mean, median, standard deviation, minimum, and maximum values. Categorical variables will be reported as frequencies and percentages. Laboratory tests as a categorical variable will be reported for shift tables. A rank ANCOVA method with adjustments for baseline value will be applied to change from baseline to Week 6 (LOCF) in serum prolactin, fasting blood glucose, HbA1c (NGSP), glycoalbumin, total cholesterol, LDL cholesterol, HDL cholesterol, triglycerides, and body weight for comparison between each SM-13496 (20-60 and 80-120 mg/day) group and the placebo group.

Laboratory data will be summarized by the flagging of abnormal values in data listings. The incidence of markedly abnormal post-baseline laboratory values (MAPLV), markedly abnormal post-baseline vital signs (MAPVS), and prolonged QTc will be summarized by treatment group. In these analyses, post-baseline laboratory test values obtained at unscheduled visits will be taken into consideration.

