16.1.7. ADDITIONAL AE SUMMARIES

- Summary of AEs by combined terms
- Summary of AEs occurring in $\geq 3\%$ of subjects. This summary will be repeated separated by country.
- Summary of AEs by exposure at earliest onset.
- Summary of AEs by preferred term by descending frequency

Document: K:\DSP\SM-13496\KVA95374\Biostatistics\Documentation\SAP

Author: [REDACTED]

Version Number:

1.0

Version Date:

30MAR2017

Template No: CS_TP_BS016 – Revision 3

Reference: CS_WI_BS005

Effective Date: 01May2012

Copyright © 2012 [REDACTED] All rights reserved.

The contents of this document are confidential and proprietary to [REDACTED]. Unauthorized use, disclosure or reproduction is strictly prohibited.

There will be no statistical comparisons between the treatment groups for safety data, unless otherwise specified with the relevant section.

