16.3. LABORATORY EVALUATIONS

Results from the central laboratory will be included in the reporting of this study for Hematology, Blood Chemistry and Urinalysis. Endocrine parameters will be summarized separately. A list of laboratory assessments to be included in the outputs is included in Table 6 of the protocol.

A LOCF endpoint will also be derived for laboratory evaluations. For calculation details, please see section 6.3.

Presentations will use reported units.

Quantitative laboratory measurements reported as "< X", i.e. below the lower limit of quantification (BLQ), or "> X", i.e. above the upper limit of quantification (ULQ), will be converted to X for the purpose of quantitative summaries, but will be presented as recorded, i.e. as "< X" or "> X" in the listings.

The following summaries will be provided for laboratory data:

- Baseline and change from baseline by visit (for quantitative measurements)
- Incidence of abnormal values according to normal range criteria (Urinalysis parameters only)
- Shift from baseline according to normal range criteria (for quantitative measurements and categorical measurements)
- Summary of subjects meeting markedly abnormal criteria (for quantitative measurements and categorical measurements)
- Listing of patients meeting markedly abnormal criteria

Additionally, the change from baseline value at LOCF endpoint for selected laboratory parameters will be evaluated using a nonparametric rank ANCOVA. For each pairwise comparison versus placebo, values of the change from baseline at LOCF endpoint and baseline values will be ranked. A linear regression will be conducted on the change from baseline ranks with baseline value rank as independent variable to produce regression residuals. Using the values of the residuals as scores, Mantel-Haenszel row mean score tests will be produced for each SM-13496 group versus placebo (Stokes, Davis, & Koch, 1995). This will be conducted for prolactin, glucose, HbA1c, and lipid tests (HDL cholesterol, LDL cholesterol, total cholesterol, and triglycerides), glycoalbumin, and HOMA-IR. Prolactin will be assessed separately by sex.

The following parameters are presented split by fasting status and overall: HDL cholesterol, LDL cholesterol, total cholesterol, insulin, triglycerides, glucose and HOMA-IR. For laboratory variables split by fasting, change from baseline will only be calculated where the post-baseline fasting status matches the baseline fasting status.

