16.5. VITAL SIGNS

The following Vital Signs measurements will be reported for this study:

- Systolic Blood Pressure (mmHg)
- Diastolic Blood Pressure (mmHg)
- Pulse Rate (bpm)
- Temperature ($^{\circ}\text{C}$)
- Weight (kg)
- BMI (kg/m^2)

The following summaries will be provided for vital signs data:

- Observed baseline and change from baseline by visit
- Incidence of markedly abnormal values
- Listing of patients meeting markedly abnormal post-baseline vital signs (MAPVS) criteria

Document: K:\DSP\SM-13496\KVA95374\Biostatistics\Documentation\SAP

Author: [REDACTED]

Version Number:

1.0

Version Date:

30MAR2017

Template No: CS_TP_BS016 – Revision 3

Reference: CS_WI_BS005

Effective Date: 01May2012

Copyright © 2012 [REDACTED] All rights reserved.

The contents of this document are confidential and proprietary to [REDACTED]. Unauthorized use, disclosure or reproduction is strictly prohibited.

Additionally, a rank ANCOVA (vs placebo) analysis will be performed for weight and BMI.

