Document:	K:\DSP\SM-13496\KVA95374\Biostatistics\Documentation\SAP	Version Number:	1.0
Author:	[REDACTED]	Version Date:	30MAR2017

Template No: CS_TP_BS016 – Revision 3
Effective Date: 01May2012

Reference: CS_WI_BS005

Copyright © 2012 [REDACTED] All rights reserved.
The contents of this document are confidential and proprietary to [REDACTED]
reproduction is strictly prohibited.

Unauthorized use, disclosure or

```
LSMEANS TRT01PN*AVISITN / DIFF=CONTROL("1", "6")diff=control("1"
"6") CL;
BY _imputation_;
RUN;
```

```
PROC MIANALYZE;
CLASS TRT01PN;
BY _TRT01PN;
MODELEFFECTS TRT01PN;
run;
```

```
proc mianalyze parms=ls_mean;
CLASS TRT01PN;
BY AVISITN;
MODELEFFECTS TRT01PN;
RUN;
```

4. MADRS 50% Responders Logistic Model

Note: Placebo will be reference

Note: All SM-13496 groups will be included in a model

```
PROC LOGISTIC DESCENDING;
CLASS TRTPN POOLSITE / PARAM=REF;
MODEL RESP50 = TRTPN POOLSITE BASE;
CONTRAST 'LUR 20-60 vs. PLACEBO' TRTPN 1 0/ESTIMATE=EXP;
CONTRAST 'LUR 80-120 vs. PLACEBO' TRTPN 0 1/ESTIMATE=EXP;
RUN;
```

5. Ranked ANCOVA (Selected Safety Parameters)

```
PROC RANK OUT= OUT1 NPLUS1 TIES = MEAN;
VAR VSCFB VSBASE;
RANKS RKVSCFB RKVSBASE;
RUN;
```

```
PROC GLM DATA = OUT1;
MODEL RKVSCFB = RKVSBASE;
OUTPUT OUT=RESIDUAL R=RESID;
RUN;
```

```
PROC FREQ DATA = RESIDUAL;
TABLES TRTPN*RESID / NOPRINT CMH2;
RUN;
```

6. NNT and 95% CI

Document: K:\DSP\SM-13496\KVA95374\Biostatistics\Documentation\SAP

Author: [REDACTED]

Version Number:

1.0

Version Date:

30MAR2017

Template No: CS_TP_BS016 – Revision 3

Reference: CS_WI_BS005

Effective Date: 01May2012

Copyright © 2012 [REDACTED] All rights reserved.

The contents of this document are confidential and proprietary to [REDACTED] reproduction is strictly prohibited.

[REDACTED] Unauthorized use, disclosure or

```
pi0a: responder rate of SM-13496 group
pi1: responder rate of placebo group
delta_ua : upper limit of NNT before taking the reciprocal
delta_la : lower limit of NNT before taking the reciprocal

nnt = round(1/(pi0a - pi1), 0.01);
delta_la = pi0a - pi1 - 1.96*sqrt(pi1*(1-pi1)/PCOUNT + pi0a*(1-
pi0a)/COUNT);
delta_ua = pi0a - pi1 + 1.96*sqrt(pi1*(1-pi1)/PCOUNT + pi0a*(1-
pi0a)/COUNT);

if pi0a>=pi1 then do;
    lower_ba = min(delta_ua, 1);
    upper_ba = max(delta_la, 0.000001);
end;
else if pi0a<pi1 then do;
    lower_ba = min(delta_ua, -0.000001);
    upper_ba = max(delta_la, -1);
end;

lcia = floor(round(1/lower_ba));
ucia = ceil(round(1/upper_ba));

* CA test */

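### For weight, prolactin, glucose and lipid measures, no planned analysis gives a difference from placebo with a confidence interval; the only between-arm result is a rank-test p-value.

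*SAP*

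**What the plan says.** Protocol section 2.2, objective 6, lists the variables whose influence is to be evaluated, for example "Body weight (change from baseline in body weight at the final assessment", together with prolactin, fasting glucose, HbA1c, glycoalbumin and four lipids. (QTc is also listed. It is outside this point because SAP section 16.4 plans no overall test of it against placebo.)

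The comparison with placebo is set out as follows.

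- Protocol section 9.7.6: "A rank ANCOVA method with adjustments for baseline value will be applied to change from baseline to Week 6 (LOCF) in serum prolactin", and likewise for the glucose and lipid measures and body weight, for each dose group versus placebo.
- SAP section 16.3: change and baseline are ranked, one set of ranks is regressed on the other, and then "Using the values of the residuals as scores, Mantel-Haenszel row mean score tests will be produced for each SM-13496 group versus placebo". On scope: "This will be conducted for prolactin, glucose, HbA1c, and lipid tests", plus glycoalbumin and HOMA-IR. Prolactin is assessed separately by sex. Glucose, lipids, insulin and HOMA-IR are presented by fasting status and overall.
- SAP section 16.5: "Additionally, a rank ANCOVA (vs placebo) analysis will be performed for weight and BMI".
- SAP Appendix 3, item 5: the last step of the sample code is "TABLES TRTPN*RESID / NOPRINT CMH2", which requests test statistics only.
- SAP section 16, general rule: "There will be no statistical comparisons between the treatment groups for safety data, unless otherwise specified with the relevant section".

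SAP section 15.2.4 uses a rank ANCOVA for the safety subgroups too.

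Two other safety outcomes are handled differently. The DIEPSS total score follows the LOCF ANCOVA of section 15.1.4.1, which reports LS mean differences with 95% CIs (section 16.7.3.1). Treatment-emergent mania gets odds ratios with 95% CIs (section 16.7.5).

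**The concern.** To evaluate an influence is to ask how large it is and how large it could still be. The protocol's background gives that question weight when it notes that "olanzapine and quetiapine are associated with adverse reactions such as increased weight and abnormal glucose metabolism". A test of no difference does not answer it. If the result is non-significant, the reader is not told which effects remain compatible with the data. If it is significant, no baseline-adjusted size comes with it.

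The SAP supplies estimates and intervals for DIEPSS and mania, so leaving them out here does not follow from a general policy on safety outcomes. What is at stake is how well the plan answers a secondary safety objective. No efficacy result depends on it.

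**Working it through.** **1. Numbers per arm.** Protocol section 3.5 gives 161 per arm for the ITT analysis (effect size 0.35, one-sided 2.5%, Hochberg, 80% chance of rejecting both hypotheses). To reproduce it: 0.35 × √(161/2) = 3.140, and 3.140 − 1.960 = 1.180. Power for one dose is Φ(1.180) = 0.881. With correlation 0.5 from the shared placebo arm, the chance that both doses succeed is 0.804 (0.802 by simulation with t statistics, 200,000 runs). The smallest n reaching 0.80 is 160, so the plan's figure stands. It was set for MADRS; the documents give no precision or power figure for any metabolic variable.

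The safety analyses use the safety population, not the ITT. The target is 167 randomised per arm, and the pooled centres in SAP Table B sum to 524, or 524/3 ≈ 175 per arm if evenly split.

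**2. Precision of an interval, if one were reported.** Half-width in SD units = 1.96 × √(2/n).

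| n per arm | Source | Half-width (SD) |
|---|---|---|
| 161 | Protocol 3.5 | 0.218 |
| 167 | randomised target | 0.214 |
| 175 | SAP Table B, 524/3 | 0.210 |
| 83.5 | prolactin within one sex, assuming 167 split 50/50 | 0.303 |

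A result with p just above 0.05 has an interval running from about zero to about 2 × 0.218 = 0.44 SD. That is true of any borderline two-arm comparison of this size, but it is the information the planned output leaves out.

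**3. In kilograms.** The documents give no SD for 6-week weight change. Over an assumed range of 1, 2, 3 and 4 kg, the half-width at 161 per arm is 0.22, 0.44, 0.66 and 0.87 kg. These figures illustrate scale only.

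**4. What the rank p-value conveys.** Ranks do not change when every value is multiplied by a positive constant. The SAP procedure was coded and run on one simulated data set (167 per arm, SD of change about 2) at three scales.

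| Scale | Rank ANCOVA p | 95% CI, unadjusted difference in mean change |
|---|---|---|
| × 0.5 | 0.42 | −0.13 to 0.30 |
| × 1 | 0.42 | −0.26 to 0.61 |
| × 2 | 0.42 | −0.52 to 1.22 |

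The p-value is the same although the effects still compatible with the data differ fourfold. It says nothing about size in the units of measurement.

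**5. What the descriptive tables allow.** From n, mean and SD by arm, the interval is difference ± 1.96 × √(s₁²/n₁ + s₂²/n₂). In the simulated set at scale 1 this gave −0.26 to 0.61, and baseline-adjusted ANCOVA also gave −0.26 to 0.61. For a roughly symmetric variable the hand calculation is serviceable. For prolactin, triglycerides and HOMA-IR, which are likely to be skewed, the tables add only the median and range (SAP section 8). They give no quartiles and no adjusted shift.

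**The case against.** The strongest reply is that information on size is planned, though not in this form. Protocol section 9.7.6 and SAP sections 8, 16.3 and 16.5 provide by-arm summaries of change, including n, mean and SD. There are also laboratory shift tables, counts of markedly abnormal laboratory values, counts of weight change of 7% or more in either direction, and a summary of metabolic TEAEs. Rank ANCOVA was pre-specified in the protocol and is a reasonable test for variables of uncertain shape. All of this stands, and it limits the consequence.

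Three stronger readings are tempting, and the documents do not support them.

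- A reader might infer that the trial cannot say how large a metabolic effect it has excluded. The by-arm summaries allow a rough interval, as shown above. What can be said is that no planned analysis states one.
- A reader might infer that SAP section 16 forbids an estimate. It limits comparisons to those specified in the relevant section, so an estimate specified in 16.3 or 16.5 would be permitted. Section 8 also defers table content to templates that are not among the public documents, so absence from the final tables is likely but not shown.
- A reader might infer that a non-significant result is meant to be reported as no influence. No section says so, no non-inferiority margin is set, and the background remark concerns other drugs.

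The reply does not meet one point: the reader is left to construct the comparison, and for the skewed variables the tables are a poor basis for it.

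**Conclusion.** The point holds as a reporting gap. For body weight, prolactin, fasting glucose, HbA1c, glycoalbumin and lipids, and for the BMI and HOMA-IR that the SAP adds, the only planned comparison with placebo is a rank test with a p-value. No estimated difference and no interval are specified in the protocol, the SAP text or the sample code.

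An interval would have a half-width of about 0.21 to 0.22 SD for variables analysed in the whole population. It would be wider for prolactin (about 0.30 SD under an assumed even sex split) and wherever the fasting-status split reduces n. These figures assume equal arms and near-complete endpoint data under LOCF.

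The change is worth making because it lets objective 6 be answered in terms of size. It concerns secondary safety objectives and leaves the primary conclusion untouched.

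**What to change.** In SAP sections 16.3 and 16.5, keep the rank ANCOVA p-value. Add, for each dose versus placebo, one pre-specified baseline-adjusted estimate with a two-sided 95% CI. Either of these would serve, provided one is chosen in advance:

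- a Hodges-Lehmann shift on the baseline-adjusted changes, for every variable; or
- an ANCOVA LS mean difference, with a ratio of geometric means from ANCOVA on log values for the skewed variables, each variable's scale being named in the SAP.

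Include BMI and HOMA-IR, report prolactin by sex, and follow the planned fasting-status split. State that the intervals are descriptive and not adjusted for multiplicity, since these variables lie outside the Hochberg procedure. Say that statements about influence will rest on the interval. Extend Appendix 3, item 5, to match, and record the addition with its reason in SAP section 3.3, as protocol section 9.1 requires. If it is made after unblinding, label it as such.

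The cost is a few lines of code and additional table columns, with no new data and no extra patients. The one drawback is that some non-significant results will visibly carry wide intervals.

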16.3.1. LABORATORY SPECIFIC DERIVATIONS

A homeostasis model assessment of insulin resistance (HOMA-IR) (Matthews, Hosker, Rudenski, Naylor, Treacher, & Turner, 1985) parameter must also be calculated and included in summaries and rank ANCOVA analyses. The calculation of the parameter is as follows:

$$\text{HOMA-IR} = \text{Glucose (mg/dL)} \times \text{Insulin (mU/L)} / 405$$

Also note that Prolactin data is considered a potential source of unblinding, so will not be available until after the study has unblinded.

16.3.2. LABORATORY REFERENCE RANGES AND MARKEDLY ABNORMAL CRITERIA

Quantitative laboratory measurements will be compared with the relevant laboratory reference ranges and categorized as:

- Low: Below the lower limit of the laboratory reference range.
- Normal: Within the laboratory reference range (upper and lower limit included).
- High: Above the upper limit of the laboratory reference range.

In addition to the high and low quantitative laboratory assignments (as identified by means of the laboratory reference ranges), markedly abnormal quantitative safety (and other) laboratory assessments will also be identified. Markedly Abnormal Post-baseline Laboratory Values (MAPLV) for selected laboratory parameters can be found in Table C. The criterion of MAPLV is satisfied if a value falls into the markedly abnormal range. Patients will be represented in the count of a particular MAPLV if they have experienced that MAPLV at least once during the post-baseline double-blind phase, regardless of baseline value, up to and including LOCF endpoint. The number and percentage of patients with MAPLV will be presented by treatment group and for the combined SM-13496 group.

Table C: Criteria for Markedly Abnormal Post-Baseline Laboratory Values

Hematology Parameter	Markedly/Abnormal Range
Hemoglobin	Male: ≤ 11.5 g/dL Female: ≤ 9.5 g/dL
Hematocrit	Male: ≤ 37% Female: ≤ 32%
WBC	≤ 2.8 x 10 ⁹ /L ≥ 16 x 10 ⁹ /L
Neutrophils (percent)	≤ 15%
Eosinophils (percent)	≥ 10%
Platelet Count	≤ 75 x 10 ⁹ /L ≥ 700 x 10 ⁹ /L
Clinical Chemistry Parameter	Markedly/Abnormal Range
Alkaline Phosphatase	≥ 3 x ULN

Document: K:\DSP\SM-13496\KVA95374\Biostatistics\Documentation\SAP
 Author: [REDACTED] Version Number: 1.0
 Version Date: 30MAR2017

Template No: CS_TP_BS016 – Revision 3 Reference: CS_WI_BS005
 Effective Date: 01May2012

Copyright © 2012 [REDACTED] All rights reserved.
 The contents of this document are confidential and proprietary to [REDACTED] Unauthorized use, disclosure or reproduction is strictly prohibited.

ALT	≥ 3 x ULN
AST	≥ 3 x ULN
Total Bilirubin	≥ 2.0 mg/dL
Albumin	< 50% LLN
Glucose (fasting)	< 45 mg/dL >160 mg/dL
Sodium	< 130 mmol/L > 150 mmol/L
Potassium	< 3 mmol/L > 5.5 mmol/L
Chloride	< 90 mmol/L > 115 mmol/L
Calcium	< 8.4 mg/dL > 11.5 mg/dL
Blood Urea Nitrogen	≥ 30 mg/dL
Creatinine	≥ 2.0 mg/dL
Creatine Phosphokinase	≥ 3 x ULN
LDH	≥ 3 x ULN
HbA1c	≥ 7.5%
Prolactin	≥ 5 x ULN
Total Cholesterol (fasting)	≥ 300 mg/dL
LDL Cholesterol (fasting)	≥ 200 mg/dL
Triglycerides (fasting)	≥ 300 mg/dL
Urinalysis Parameter	Markedly Abnormal Range
RBC	> 25 hpf
WBC	> 25 hpf

